- e Sample to be collected at any time ≤ 3 days prior to the infusion. IMC-CS4 may be administered as planned while troponin (I or T) results are pending, provided no cardiac symptoms have been revealed upon ECG or physical examination.
- f Analysis to be performed only if serum enzymes are $\geq 2.5 \times$ ULN at Week 5 of previous cycle.
- g Analysis to be performed only if serum CK levels are $\geq 2.5 \times$ ULN at Week 5 of previous cycle. IMC-CS4 may be administered as planned while troponin (I or T) results are pending, provided no cardiac symptoms have been revealed upon ECG or physical examination.
- h For subjects who proceed to Cycles 4 to 6, blood samples will be collected prior to the last infusion of each cycle. In the event that a subject does not proceed to these cycles, these samples will not be collected.
- i A sample will be collected 30 days after last dose of investigational agent, regardless of duration of therapy.

Note: If at any time a subject experiences an infusion-related reaction to IMC-CS4, all attempts will be made to obtain a blood sample for immunogenicity analysis as close to the onset of the event as possible, at the resolution of the event, and 30 days following the event. A portion of the sample taken for immunogenicity testing may be used for PK analysis, in the setting of infusion-related reactions.

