2.2 Secondary Objectives

The secondary objectives of this study are:

- Part A only – To define the recommended Phase 2 dose (RP2D) using weight-based dosing;
- Part B only – To define the RP2D using non-weight-based dosing;
- To characterize the pharmacodynamic profile of IMC-CS4 on circulating levels of CSF-1; and
- To assess the development of antibodies against IMC-CS4 (immunogenicity).

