6.8.2 Immunogenicity Testing (Anti-IMC-CS4 Antibodies)

Blood samples for the assessment of antibodies against IMC-CS4 (immunogenicity) will be collected for all study subjects at specified time points throughout the study (Section 7.7). In addition, if a subject should have an infusion-related reaction to IMC-CS4, all attempts will be made to obtain a blood sample for immunogenicity analysis as close to the onset of the event as possible, at the resolution of the event, and 30 (calendar) days following the event. For each specified time point, one tube (approximately 7.5 mL/tube) of blood is required; if the timing of a PK sample should coincide with that of an immunogenicity sample, the same sample will suffice for both studies.

In certain circumstances, including if antibodies against IMC-CS4 are detected, the subject's serum IMC-CS4 concentration will be analyzed using the same sample, in order to determine if there is any alteration of IMC-CS4 PK. Detailed instructions for collecting, processing, storing, and shipping of samples will be provided by the Sponsor and its representative(s)/delegate(s) in a separate procedure manual. Refer to Section 7.7 for a detailed schedule of collection time points.

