7.7 Pharmacokinetic and Other Sampling

Table 7, Table 8, and Table 9 summarize PK and other sampling scheduled to occur as part of Study IMCL CP24-1001.

Table 7. Blood Collection Schedule (Parts A and B - Weekly Cohorts 1, 2, 3, 5, 6a, 6c, 7a, 7c, 8a, and 8c)

Blood Collection Time Point ^a	Analyses						
	PK ^b	IGx ^b	PD	FC	Iso	Trop	Bone
Pretreatment							
Prior to the first infusion	X ^c	X ^d	X ^d	X ^d	X ^d	X ^d	X ^d
Cycle 1 (Week 1)							
Immediately after the end of the first infusion of Cycle 1	X						
1 hr after the end of the first infusion	X		X				
2 hr after the end of the first infusion	X		X				
4 hr after the end of the first infusion	X		X				
24 hr (Day 2) after the end of the first infusion	X		X	X			
48 hr (Day 3) after the end of the first infusion	X		X	X			
72 hr (Day 4) after the end of the first infusion	X		X	X			
168 hr (Day 8) after the end of the first infusion immediately (unless otherwise footnoted) prior to the second infusion of Cycle 1	X	X	X	X	X ^e	X ^e	X ^e
Cycle 1 (Week 3)							
Immediately (unless otherwise footnoted) prior to the third infusion of Cycle 1				X	X ^e	X ^e	
Cycle 1 (Week 4)							
Immediately (unless otherwise footnoted) prior to the fourth infusion of Cycle 1	X	X	X	X			X ^e
Cycle 2 (Week 1)							
Prior to the first infusion of Cycle 2					X ^f	X ^g	
Cycle 2 (Week 6)							
Immediately prior to the sixth infusion of Cycle 2	X		X				
Cycle 3 (Week 1)							
Immediately prior to the first infusion of Cycle 3	X	X	X				
Immediately after the end of the first infusion	X						
1 hr after the end of the first infusion	X		X				
2 hr after the end of the first infusion	X						
4 hr after the end of the first infusion	X		X				
24 hr (Day 2) after the end of the first infusion	X						
48 hr (Day 3) after the end of the first infusion	X						
96 hr (Day 5) after the end of the first infusion	X						
168 hr (Day 8) after the end of the first infusion, immediately (unless otherwise footnoted) prior to the second infusion of Cycle 3	X		X	X			X ^e
Cycle 3 (Week 4)							
Immediately prior to the fourth infusion of Cycle 3	X	X	X				
Cycles 4-6^h							
Prior to the last infusion of each cycle	X		X				

Table is continued on the next page.

Table 7. Blood Collection Schedule (Parts A and B - Weekly Cohorts 1, 2, 3, 5, 6a, 6c, 7a, 7c, 8a, and 8c)

Blood Collection Time Point ^a	Analyses						
	PK ^b	IGx ^b	PD	FC	Iso	Trop	Bone
Cycle 5							

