Immediately prior to the first infusion of Cycle 5 (6 months after the first infusion of Cycle 1)		X					
End of Therapy							
At the End-of-Therapy visit					X ^f	X ^g	
Follow-up							
30-Day Follow-up visit ⁱ	X	X	X	X	X ^f	X ^g	

Abbreviations: Bone = assessment of bone metabolism markers (CTX-I and P1NP); CK = creatine kinase; CTX-I = C-terminal cross-linking telopeptide of type I collagen; ECG = electrocardiogram; FC = flow cytometry analysis; IGx = immunogenicity; Iso = isoenzyme analysis; P1NP = procollagen type 1 N-terminal propeptide; PD = pharmacodynamic markers; PK = pharmacokinetic(s); Trop = troponin (I or T) assessment; ULN = upper limit of normal.

- a It is understood that it may not be feasible to collect samples at precise intervals following the end of the infusions. Every attempt should be made to collect each of these samples as close to the time point as possible. The date and time of all PK samplings must be clearly and accurately recorded.
- b PK samples will be collected from all subjects. The date and time of all samplings must be clearly and accurately recorded. The blood samples collected for PK will also be used for immunogenicity analyses. For each specified time point, 1 tube of blood is required to be drawn for any combination of PK or immunogenicity analyses. As an example, if the timing of a PK sample should coincide with that of an immunogenicity sample, the same sample will suffice for these studies and the same total amount of blood (1 tube, approximately 7.5 mL/tube) will be collected.
- c Pretreatment sampling should be collected on the day of and immediately prior to the first infusion.
- d IGx, PD, FC, isoenzyme analysis, and bone metabolism markers: Sample to be collected ≤ 7 days prior to the first infusion of Cycle 1. Troponin (I or T) analysis: Sample to be collected prior to the first infusion of Cycle 1 so that results are obtained before dosing.
- e Sample to be collected at any time ≤ 3 days prior to the infusion. IMC-CS4 may be administered as planned while troponin (I or T) results are pending, provided no cardiac symptoms have been revealed upon ECG or physical examination.
- f Analysis to be performed only if serum enzymes are $\geq 2.5 \times$ ULN at Week 5 of Cycle 1.

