- g Analysis to be performed only if serum CK levels are $\geq 2.5 \times$ ULN at Week 5 of Cycle 1. IMC-CS4 may be administered as planned while troponin (I or T) results are pending, provided no cardiac symptoms have been revealed upon ECG or physical examination.
- h For subjects who proceed to Cycles 4 to 6, blood samples will be collected prior to the last infusion of each cycle. In the event that a subject does not proceed to these cycles, these samples will not be collected.
- i A sample will be collected 30 days after last dose of investigational agent, regardless of duration of therapy.

Note: If at any time a subject experiences an infusion-related reaction to IMC-CS4, all attempts will be made to obtain a blood sample for immunogenicity analysis as close to the onset of the event as possible, at the resolution of the event, and 30 days following the event. A portion of the sample taken for immunogenicity testing may be used for PK analysis, in the setting of infusion-related reactions.

Table 8. Blood Collection Schedule (Part A - Every-2-Week Cohort 4)

Blood Collection Time Point ^a	Analyses						
	PK ^b	IGx ^b	PD	FC	Iso	Trop	Bone
Pretreatment							
Prior to the first infusion	X ^c	X ^d	X ^d	X ^d	X ^d	X ^d	X ^d
Cycle 1 (Week 1)							
Immediately after the end of the first infusion of Cycle 1	X						
1 hr after the end of the first infusion	X		X				
2 hr after the end of the first infusion	X		X				
4 hr after the end of the first infusion	X		X				
24 hr (Day 2) after the end of the first infusion	X		X				
72 hr (Day 4) after the end of the first infusion	X		X	X			
168 hr (Day 8) after the end of the first infusion	X		X				
336 hr (Day 15) after the end of the first infusion, immediately (unless otherwise footnoted) prior to the second infusion of Cycle 1	X	X		X	X ^e	X ^e	X ^e
Cycle 1 (Week 3)							
Immediately after the end of the second infusion of Cycle 1	X						
1 hr after the end of the second infusion	X		X				
2 hr after the end of the second infusion	X		X				
4 hr after the end of the second infusion	X		X				
24 hr (Day 2) after the end of the second infusion	X		X				
72 hr (Day 4) after the end of the second infusion	X		X				
168 hr (Day 8) after the end of the second infusion	X		X				
336 hr (Day 15) after the end of the second infusion (Week 5)	X		X				
504 hr (Day 22) after the end of the second infusion (Week 6) of Cycle 1	X		X				
Cycle 2 (Week 1)^h							
Prior to the first infusion of Cycle 2					X ^f	X ^g	

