12 PLANNED STATISTICAL METHODS

12.1 General Considerations

Statistical analysis of this study will be the responsibility of the Sponsor.

The interpretation of the study results will be the responsibility of the investigators with the Lilly CRP or CRS, pharmacokineticist, and statistician. The CRP or CRS and statistician will also be responsible for the appropriate conduct of an internal review for both the final study report and any study-related material to be authorized by Lilly for publication.

The analyses for this study will be descriptive, except for possible exploratory analyses as deemed appropriate. Data analyses will be provided by dose levels and for all subjects combined, wherever appropriate. For continuous variables, summary statistics will include number of subjects (N), mean, median, standard deviation, minimum, and maximum. Categorical endpoints will be summarized using N, frequency, and percentages. Missing data will not be imputed. Exploratory analyses of the data that are not described in the protocol will be conducted as deemed appropriate. A detailed description of data analyses will be provided in a separate statistical analysis plan document for this study.

This is a Phase 1 study with an open-label, dose-escalation design. Subjects will be enrolled into cohorts sequentially without randomization to dose level. During dose escalation, the total sample size per cohort will be guided by the standard oncology 3+3 method and determined by the occurrences of DLTs for the treated subjects. The total sample size for Parts A and B is estimated to be approximately 72 treated subjects. In Part A, the sample size is estimated to be approximately 30 subjects. In Part B, the sample size is estimated to be approximately 9 to 42 subjects.

Pretreatment and posttreatment anti-IMC-CS4 samples will be assayed using an immunoassay. A sample will be considered positive for IMC-CS4 antibodies if it exhibits a postbaseline antibody level that exceeds the upper 95% confidence interval of the mean determined from the normal anti-IMC-CS4 level seen in healthy untreated individuals.

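### From the last infusion of Cycle 4 onward, antibody sampling is denser in Table 9 than in Tables 7 and 8, with no stated reason, although PK blood is drawn at the same visits

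*Protocol*

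**What the plan says.** The development of antibodies to IMC-CS4 is a secondary objective (Protocol 2.2). Sampling is set out in Section 7.7: Table 7 for all weekly cohorts in Parts A and B, Table 8 for the every-2-week Cohort 4, and Table 9 for Cohorts 6b, 7b and 8b.

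Each table has a Cycles 4-6 row worded "Prior to the last infusion of each cycle". Its marks are:

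| Table | PK | Immunogenicity | Pharmacodynamics |
|---|---|---|---|
| 7 | yes | no | yes |
| 8 | yes | no | yes |
| 9 | yes | yes | yes |

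Footnote b to each table states: "The blood samples collected for PK will also be used for immunogenicity analyses". Section 6.8.2 adds that "if the timing of a PK sample should coincide with that of an immunogenicity sample, the same sample will suffice for both studies". Footnote h to Tables 7 and 9 limits the Cycles 4-6 samples to subjects who get that far: "In the event that a subject does not proceed to these cycles, these samples will not be collected". All three tables schedule an antibody sample before the first infusion of Cycle 5 and another at follow-up: "A sample will be collected 30 days after last dose of investigational agent, regardless of duration of therapy".

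Positivity is defined sample by sample in Section 12.1, against the average level in untreated healthy people: "A sample will be considered positive for IMC-CS4 antibodies if it exhibits a postbaseline antibody level that exceeds the upper 95% confidence interval of the" (the quote stops just short of naming that average). Neither document gives a rule for calling a subject positive. The SAP lists an antibody table (14.3.26) and a listing (29) without describing a method.

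**The concern.** The three tables cover the same drug, objective and assay, and the blood is drawn at these visits in every cohort. Yet only Table 9 tests it for antibodies. Nothing in either document explains why.

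Two things are at stake. First, with positivity defined per sample and no subject-level rule, an ever-positive count will tend to rise with the number of samples tested. Late sampling intensity differs along the line that separates a b cohort from its a cohort, which receives the same dose weekly; the two will sit next to each other in descriptive tables. Second, Section 6.8.2 provides for measuring drug concentration in an antibody-positive sample, to see whether the antibody has altered PK. PK is part of the primary objective. In weekly cohorts the Cycles 4-6 troughs have no scheduled antibody result from the same tube, so a falling trough would be harder to interpret.

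**Working it through.** The plan states no figure here, so the check is a count of the immunogenicity marks in the current Tables 7, 8 and 9.

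**Scheduled post-baseline antibody samples**

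- Table 7: Cycle 1 before infusions 2 and 4; Cycle 3 before infusions 1 and 4; Cycle 5 before infusion 1; 30-day follow-up. Total 2 + 2 + 1 + 1 = 6.
- Table 8: Cycle 1 before infusion 2; Cycle 3 before infusions 1 and 3; Cycle 5 before infusion 1; follow-up. Total 1 + 2 + 1 + 1 = 5.
- Table 9: Cycle 1 before infusions 2 and 4; Cycle 3 before infusions 1 and 3; Cycle 5 before infusion 1; last infusion of Cycles 4, 5 and 6; follow-up. Total 2 + 2 + 1 + 3 + 1 = 9.

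By last cycle completed, counting the follow-up sample:

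| Treated through | Table 7 | Table 8 | Table 9 |
|---|---|---|---|
| Cycle 1 or 2 | 3 | 2 | 3 |
| Cycle 3 | 5 | 4 | 5 |
| Cycle 4 | 5 | 4 | 6 |
| Cycle 5 | 6 | 5 | 8 |
| Cycle 6 | 6 | 5 | 9 |

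Tables 7 and 9 part company only at the last infusion of Cycle 4. Table 8 is one sample lower from Cycle 1, a separate difference.

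**Where the gap falls in weekly cohorts.** With 6-week cycles and six infusions each, the last infusions of Cycles 4, 5 and 6 fall in Weeks 24, 30 and 36, and Cycle 5 starts in Week 25. The unmarked Week 24 sample is one week before a scheduled one and adds little. After Week 25 nothing is scheduled until 30 days after the last dose. For a subject whose last dose is the Week 36 infusion, that is 11 × 7 + 30 = 107 days, about 15 weeks, spanning 12 infusions.

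**Illustration of size.** The documents give no per-sample positivity rate p. Assume p from 1% to 10% and independent samples. The chance of at least one positive in k samples is 1 − (1 − p)^k. For a subject treated through Cycle 6:

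| p | Table 7, k = 6 | Table 8, k = 5 | Table 9, k = 9 | Table 9 minus Table 7 |
|---|---|---|---|---|
| 1% | 5.9% | 4.9% | 8.6% | 2.7 points |
| 2.5% | 14.1% | 11.9% | 20.4% | 6.3 points |
| 5% | 26.5% | 22.6% | 37.0% | 10.5 points |
| 10% | 46.9% | 41.0% | 61.3% | 14.4 points |

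Independence is unfavourable: positives that persist within a subject would be expected to narrow the gap. In the limit, an antibody still present at follow-up is found under every table and the gap is zero. In head-count terms, a b cohort of 6 (the upper end of the 3 to 6 in Section 4.1), all reaching Cycle 6, would differ by 6 × 0.105 = 0.6 subjects at p = 5%. If expanded to the 12 evaluable subjects that Section 4.1 allows at the MTD, the figure is 12 × 0.105 = 1.3.

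**The case against.** A reader might infer that antibody incidence cannot be compared across schedules at all, or that late antibodies in weekly cohorts would go undetected. The documents support neither.

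- Tables 7 and 9 schedule the same number of antibody samples through Cycle 3, so early incidence is on an equal footing between them.
- All three tables sample before Cycle 5 and at follow-up, and also call for samples around any infusion-related reaction. A late antibody that persists should be caught in any cohort, provided the follow-up sample is obtained.
- Analyses are descriptive (Section 12.1), and neither document plans a between-schedule contrast of antibody incidence. Cohorts are not randomised. A b cohort opens only after at least 2 DLTs in the matching a cohort, so none may enrol.
- The percentages above rest on assumed rates and independence and should not be read as a predicted bias.
- Footnote b, taken literally, could mean that every PK tube is tested for antibodies, which would remove the gap.

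The first four points stand and limit the concern to late sampling. The fifth does not remove it: if every PK tube were to be tested, a separate immunogenicity column would have no purpose, and Table 9 would not need its extra marks. The footnote and the column need to agree. The long on-treatment gap in Table 7 exists whether or not a b cohort opens.

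**Conclusion.** The point holds as a minor one. From the last infusion of Cycle 4, antibody sampling is uneven across schedules without a stated reason: 6, 5 and 9 scheduled post-baseline samples through Cycle 6 in Tables 7, 8 and 9. The likely loss in weekly cohorts is transient positives, the timing of onset between Week 25 and follow-up, and antibody results paired with the Cycles 4-6 troughs. Persistent late antibodies should not be lost.

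The counts come straight from the tables. The effect on an ever-positive rate cannot be fixed from the documents: through Cycle 6 it lies between nothing, if antibodies persist to follow-up, and roughly 3 to 14 percentage points for assumed per-sample rates of 1% to 10% with independent samples. It applies only to subjects who reach the end of Cycle 4. The documents do not say how many that will be; in refractory advanced disease it is likely to be few.

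**What to change.** 1. Add an immunogenicity mark to the Cycles 4-6 row of Table 7, run on the PK tube already drawn. This brings Table 7 from 6 to 9 samples through Cycle 6, equal to Table 9, and breaks the long gap at Weeks 30 and 36.
2. Do the same in Table 8 for any Cohort 4 subject still on treatment. Table 8 would rise from 5 to 8, still one short because it has one fewer Cycle 1 sample. The value is limited, since Section 4.1 planned to end Part A enrolment on 30 September 2015.
3. State in footnote b whether antibody testing is confined to the marked time points.
4. In the SAP, base any side-by-side summary of subject-level antibody incidence on time points common to the tables being compared, and report the number of samples tested per subject. Common to all three are: before infusion 2 of Cycle 1, before infusion 1 of Cycle 3, late Cycle 3, before infusion 1 of Cycle 5, and follow-up. Tables 7 and 9 also share the sample before infusion 4 of Cycle 1.

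The cost is up to three extra assays per subject reaching Cycle 6, with no added blood draw. The decision should be made while the tubes exist: Section 6.8 keeps PK samples for at most 1 year after the last subject visit, against 15 years for immunogenicity samples.

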8 ADVERSE EVENTS ASSESSMENTS

Investigators are responsible for monitoring the safety of subjects who have entered this study and for alerting the Sponsor or its designee to any event that seems unusual, even if this event may be considered an unanticipated benefit to the subject.

The Investigator is responsible for the appropriate medical care of subjects during the study.

The Investigator remains responsible for following, through an appropriate health care option, AEs that are serious or are reportedly related to study treatment or that caused the subject to discontinue treatment before completing the study. The subject should be followed until the event is resolved, the event is no longer considered to be drug-related, the event becomes stabilized or returns to baseline, the event is deemed irreversible or otherwise explained, a new treatment is initiated for the subject, or the subject dies or is lost to follow-up. Frequency of follow-up evaluation is left to the discretion of the Investigator.

The timing of all safety evaluations is shown in the study schedule (see Section [7.6](#)).

8.1 Adverse Events

The Sponsor has standards for reporting AEs that are to be followed regardless of applicable regulatory requirements that may be less stringent. A clinical study AE is any untoward medical occurrence in a patient or clinical investigation subject administered a pharmaceutical product and which does not necessarily have a causal relationship with this treatment. Any clinically significant findings from ECGs, laboratory assessments, vital sign measurements, or other procedures that result in a diagnosis should be reported to the Sponsor or its designee.

Lack of drug effect is not an AE in clinical trials, because part of the purpose of a clinical trial is to establish drug effect.

Cases of pregnancy that occur during maternal or paternal exposures to study treatment and up to 12 weeks following last study treatment dose should be reported immediately. Data on fetal outcome and breastfeeding are collected for regulatory reporting and drug safety evaluation.

For all entered subjects, study site personnel will record the occurrence and nature of each subject's preexisting conditions, including clinically significant signs and symptoms of the disease under treatment in the study. While the subject is on study, site personnel will record any change in these preexisting condition(s) and the occurrence and nature of any AEs. In addition, all AEs related to protocol procedures are reported to the Sponsor or designee.

In addition, all AEs occurring after the subject receives the first dose of study treatment until 30 days following the discontinuation of study treatment must be reported to the Sponsor or its designee via eCRF.

Investigators will be instructed to report to the Sponsor or its designee their assessment of the potential relatedness of each AE to protocol procedure or investigational product via eCRF.

The Investigator will decide whether he or she interprets the observed AEs as related to disease, to the study medication, study procedure, or other concomitant treatment or pathologies. To assess the relationship of the AE to the study drug or procedure, the following terminologies are defined:

- **Probably related:** A direct cause and effect relationship between the study treatment and the AE is likely.
- **Possibly related:** A cause and effect relationship between the study treatment and the AE has not been demonstrated at this time and is not probable, but is also not impossible.
- **Does not know:** The Investigator cannot determine.
- **Not related:** Without question, the AE is definitely not associated with the study treatment.

All "probably related," "possibly related," or "does not know" AEs will be defined as related to study drug/study procedure.

Subjects will be evaluated for AEs at each visit and will be instructed to call their study physician to report any AEs between visits.

NCI-CTCAE, Version 4.0 will serve as the reference document for grading the severity of all AEs and other symptoms. For AEs without matching terminology within the NCI-CTCAE, Version 4.0, the Investigator will be responsible for selecting the appropriate System Organ Class and assessing severity grade based on the intensity of the event.

In addition to collecting the AE verbatim and NCI-CTCAE severity grade, AE verbatim text will also be mapped by the Sponsor or designee to corresponding terminology within the Medical Dictionary for Regulatory Activities (MedDRA®).

If a subject's dosage is reduced or treatment is discontinued as a result of an AE, study site personnel must clearly report to the Sponsor or its designee via eCRF the circumstances and data leading to any such dosage reduction or discontinuation of treatment.

